5.4.6 Rapid HIV Testing, Confirmatory Testing, and False Positives

As previously indicated, participants will be asked to provide a separate consent for HIV testing if necessary depending on local/state guidelines. On-site rapid HIV testing will be conducted using a test such as the OraQuick ADVANCE Rapid HIV-1/2 Antibody test (hereafter referred to as "rapid HIV test"). OraQuick rapid test is a single-use, test using whole blood to detect HIV antibodies. It has 99.6% sensitivity and 100% specificity. The rapid HIV test is intended for use as point-of-care test to assist in the diagnosis of infection with HIV-1 and HIV-2. It is easy to perform with a negligible chance of error and, therefore, is CLIA-waived.

Participants whose test result is reactive (also known as "preliminary positive") will receive a confirmatory HIV blood test that day. With a target sample size of approximately 5,000 study participants, some discordant results between the initial reactive rapid test and follow-up tests may occur. In this case, and per FDA guidelines, the follow-up test will be considered the gold standard for diagnosing HIV infection. During the study consent process, HIV testing consent process (as applicable) and the testing and counseling session (in both arms), participants will be advised of the possibility and meaning of discordant test results. STD clinics will follow the local/state standard for reporting positive HIV results, and participants will be notified of these guidelines as part of the informed consent process.

Additionally, participants whose test result is preliminary positive will receive the current standard of care: participants will be informed of their preliminary positive test result in a confidential face-to-face manner, receive counseling and referrals, and will receive a confirmatory HIV test (additional information is provided on the counseling for persons who test HIV positive in section 6.3 of the protocol). For this confirmatory HIV test, counselors will collect additional blood using a needle and test tube. The second sample will be sent to an external laboratory that will perform a supplemental test which will serve as confirmation of the participants' HIV status. Participants will be scheduled to return for the result of the confirmatory test approximately 5-10 days after providing the sample. We will try to follow-up these individuals if they do not return for their test results. Study participants may refuse confirmatory HIV testing. If this occurs, participants will be asked to consider confirmatory testing at some specific future date with confirmatory testing to be conducted by study counselor, another testing site, or a medical provider. The main study consent addresses confirmatory testing so no additional consenting will be needed for confirmatory testing. Confirmatory test results will be recorded on study CRFs which will include participant ID numbers, but not names. Confirmatory test results will also be placed in medical records.

With a target sample size of approximately 5,000 study participants, some false positives may occur. During both the HIV testing consent process and the testing and counseling session participants will be advised of the possibility and potential meaning of testing false positive. The HIV testing consent will contain clear language discussing the possibility and potential meaning of receiving a false positive test result. Participants receiving a false positive test result will be referred to a medical provider for further testing including HAV, HBV, and HCV. Participants will be encouraged to contact research counselors if they need additional support or referrals around the false positive result.

Any confirmatory test result that is indeterminate or negative will be repeated in one month per CDC guidelines.

5.4.7 Safety Assessments

Adverse events will be captured post-randomization as described in section 7.11.

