In both Groups 1 and 2, participants who test reactive (preliminary positive) will be counseled on the sexual risk behaviors associated with transmission of HIV and the acquisition of STIs, as is current clinical practice with those testing HIV-positive (Branson et al., 2006). In addition, the importance of receiving ongoing HIV primary medical care and referral to care and case management services will be included (Walensky, Weinstein, Smith, Freedberg, & Paltiel, 2005). All participants testing invalid or reactive on the rapid test will receive a confirmatory HIV blood test that day, with results delivered 5-10 days later. The study staff will work to ensure that the confirmatory test is conducted and the result given to the participant.

[figure not shown]
All participants will provide informed consent prior to their involvement in the protocol. Additionally, depending on local HIV testing guidelines, participants may also be required to provide a second consent in order to proceed with HIV testing.

[figure not shown]
Safety Assessment: There will be ongoing monitoring of adverse events. Adverse events will be collected at each research visit.

Outcomes: There is one primary outcome for this study. The outcome is composite STI incidence at 6-month follow-up in which a person is considered positive for STIs if they are positive on any tested STI. Secondary outcomes will include self-reported sexual risk behavior, being under the influence of substances and/or illicit drug use during sexual activity and cost and cost-effectiveness.

Analysis: The primary outcome will be analyzed using logistic regression for the binary outcome, new diagnoses of STIs (Yes/No). The logistic regression analysis will predict 6-month STI incidence as a function of randomization group controlling for the baseline incidence of STI. ANCOVA will be used for the secondary continuous outcomes, number of sexual risk behaviors and number of sexual episodes involving substance use. Costs will be compared based on study records supplemented by site-level data collection (detailed further in Section 10.4). Primary analyses will be performed under intent-to-treat (ITT) criteria.

Regulatory Issues: The trial will be conducted in compliance with protocol, International Conference of Harmonization (ICH) guidelines for Good Clinical Practice (GCP), and applicable federal, state, and local regulatory requirements.

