Depression: We will use the Center for Epidemiologic Studies-Depression Short Depression Scale (CES-D 10) which is a shorter version of the CES-D (Radloff, 1977). The CES-D was developed to measure symptoms of depression in community populations and measures depressive feelings and behaviors during the past week, with questions ranging from depressed mood, feelings of worthlessness, feelings of hopelessness, loss of appetite, poor concentration, and sleep disturbance. The CES-D 10 has demonstrated good predictive accuracy when compared to the full-length 20-item version of the CES-D and has shown an expected positive correlation with poorer health status scores and a strong negative correlation with positive affect (Andresen, Malmgren, Carter & Patrick, 1994) Subjects are asked to rate each item on a scale from 0 to 3 on the basis of "how often you have felt this way during the past week": 0 = rarely or none of the time (less than 1 day), 1 = some or a little of the time (1–2 days), 2 = occasionally or a moderate amount of time (3–4 days), and 4 = most or all of the time (5–7 days).

Tak Schedule of Study Acti	ole 1 vities and Ass	essments	
Study Activities/Measures	Screen	Baseline	6-month Follow-up
Verbal Informed Consent	Х		
Screening	Х		
Written Informed Consent		Х	
Locator Information Form		Х	Х
HIPAA Form and/or Medical Record Release Form		Х	
STI Testing		Х	Х
Group 1 or 2 Intervention		Х	
HIV testing Informed Consent (as applicable)		Х	
HIV Testing		Х	Х
Visit with clinician and STI/HIV treatment (as applicable)		Х	Х
Exit Interview		Х	
Medical Record Release Forms (as applicable for HIV primary care)			Х
Randomization		Х	
*Medical Record Abstraction		Х	Х
The below measures (Demographics through Smoking) are	e captured via t	he ACASI	
Demographics	Х	Х	
Global sex behaviors		Х	Х
HIV and STI Testing Behavior		Х	Х
Attitudes Toward HIV Testing		Х	X
Readiness for HIV testing		Х	Х
Readiness to use condoms		Х	Х
Attitudes toward safer sex		Х	Х
Global substance use		Х	Х
Injection risk behavior		Х	Х
Intervention Exposure	1		Х

Depression	Х	Х			
Utilization of Health Care	Х	Х			
Utilization of HIV Care for Persons who test Positive		Х			
Alcohol and Substance use	Х	Х			
Smoking	Х	Х			
AEs/SAEs	To be collected any time post-randomization.				
Study Completion	To be collected upon formal drop out, investigator's removal or participant's study end date.				

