7.11 Adverse Events (AE)

Adverse events (AE), defined as any reaction, side effect, or untoward event that occurs during the course of the clinical trial, whether or not the event is considered clinically significant, will only be reported if considered related to the study intervention(s). A new illness, symptom, sign or worsening of a pre-existing condition or abnormality is considered an AE. Stable chronic conditions, such as arthritis, which are present prior to clinical trial entry and do not worsen are not considered AEs. All reportable AEs must be submitted on the AE eCRF. The AE eCRF is also used to record follow-up information for unresolved events reported on previous visits. A site principal investigator will classify each AE as serious or non-serious and follow appropriate reporting procedures.

For the purpose of this study, only the following events will be required for reporting as AEs:

- Only medical events that are directly related to the collection of the HIV and STI test samples (e.g. irritation at the testing site); and
- Additional adverse events to be reported in the database for this study will be assessed based on report of untoward events that the participant or investigator believes are a direct result of the study intervention or assessments. Events reported that are considered

unrelated to study procedures by BOTH the participant and the investigator will not be reported as AEs.

Other safety information is based on spontaneous reports and not specifically required by the study team. The benefits to this system will include safety reporting to assess the effects of the intervention on the study population, reducing reporting burden on the sites, reducing duplicative data entry of events (reporting the same event on a clinical assessment form and an adverse event form), which eliminates the need to reconcile the same data reported in two locations.

Definition of a Serious Adverse Event (SAE)

A serious adverse event (SAE) is defined as any untoward physical or psychological occurrence during the study that suggests a significant hazard, side effect, or precaution.

This protocol will only require SAE reporting of any deaths that occur during study participation and of any other events meeting the criteria defined below if the investigator or the participant believes the event is related to the participant's role in the study.

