This study is using a standard definition of SAE categories, which includes, but is not limited to any of the following events:

- Death: A death occurring during the study or which comes to the attention of the investigator during the protocol-defined follow-up after the completion of treatment, whether or not considered treatment-related, must be reported
- Life-threatening: Any adverse therapy experience that places the participant or participants, in the view of the investigator, at immediate risk of death from the reaction as it occurred (i.e., it does not include a reaction that, had it occurred in a more serious form, might have caused death)
- In-patient hospitalization or prolongation of existing hospitalization
- Persistent or significant disability or incapacity
- Congenital anomaly/birth defect
- An event that required intervention to prevent one of the above outcomes

Events that do not meet any of the above criteria and are not considered related to study procedures will not be reported as SAEs.

Additionally, for the purpose of this study, the following will **not** be considered SAEs:

- Admission to a hospital/surgery center for preplanned/elective surgeries;
- Admission to a hospital for scheduled labor and delivery.

Eliciting and Monitoring Adverse Events

Appropriate research staff will elicit participant reporting of AEs/SAEs. Adverse events (medical and/or psychiatric) will be collected starting after participant randomization and at the 6-months follow-up visit. The research staff will obtain as much information as possible about the AE/SAE to complete the AE/SAE forms and will consult with designated staff as warranted. A site

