10.2 Randomization

Participants will be randomized to one of two treatment groups. Randomization will be stratified by site and within site, by race/ethnicity, gender and within males, by MSM versus heterosexual. The randomization procedure will be conducted in a centralized process through the Duke Clinical Research Institute (DCRI). Specifically, randomization schedules will be created by the study statistician for each randomization stratum within each site. The race/ethnicity categories will include: African American, Hispanic, European American, and other). Note that Hispanics of African origin will be classified as Hispanic for the purpose of randomization. The randomization schedules will be of a randomized-block nature to ensure relative equality of assignment across condition across the recruitment period and to prevent the potential for study staff quessing the next assignment which is heightened when a fixed block-size is used. After providing Informed Consent and subsequently completing the baseline assessment on ACASI and the STI testing, the site research coordinator (or designee) will perform the randomization. The research coordinator will contact the central randomization center to determine the appropriate condition for the site. The method of this notification will be by computer-assisted telephone. The research coordinator will enter the appropriate participant characteristics (site, participant ID, gender and ethnicity) by pushing appropriate telephone buttons. The treatment assignment will then be transmitted by computer voice (by telephone) and by fax or computer screen. The DCRI statistician will review the randomization data on a regular basis to ensure that the scheme is being implemented according to plan.

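### Adverse-event capture starts at randomization, but the described order puts baseline STI sampling, whose events are reportable, before it

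*Protocol*

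**What the plan says.** **What is reportable.** Section 7.11 restricts AE reporting to two groups. The first is "Only medical events that are directly related to the collection of the HIV and STI test samples". The second is events that the participant or the investigator attributes directly to the intervention or the assessments. The definition of definite relatedness in 7.11 also refers to the STI tests.

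**When capture starts.** Section 5.4.7: "Adverse events will be captured post-randomization as described in section 7.11". Section 7.11: events "will be collected starting after participant randomization and at the 6-months follow-up visit". The AE/SAE row of Table 1: "To be collected any time post-randomization". The synopsis differs and mentions no randomization limit: "Adverse events will be collected at each research visit".

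**When STI samples are taken.** Section 10.2 gives this order: after consent and "subsequently completing the baseline assessment on ACASI and the STI testing, the site research coordinator (or designee) will perform the randomization". Section 5.1 has the same sequence of consent, STI testing, ACASI and randomization. Section 5.4 lets a participant have consent and STI testing at one visit and randomization at a second. Section 5.4.3 describes the samples: blood from everyone, vaginal specimens from women, rectal and urine specimens from MSM, and urine from other men.

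**What loosens that order.** The synopsis calls the order flexible and fixes three conditions, none of which puts STI testing before randomization. Section 5.3.3 lets verified tests from the same day's routine clinic visit stand in for study samples.

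**The concern.** The protocol keeps AE reporting narrow and names sample collection first among the reportable sources. The stated collection window then opens after one of the main sampling occasions has, in the described order, already taken place. A short-lived reaction to a blood draw or swab that is over before randomization has no instruction covering it. Nor has any event in someone who consents, gives samples and is never randomized. The DSMB, which reviews accumulating safety data (section 7.8), would then see sampling events sought at the time of sampling at the 6-month visit but not at the baseline STI collection.

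**Working it through.** The protocol gives no figure for safety capture, so there is none to reproduce. The check is a count of sampling occasions.

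**Inputs**
- Number randomized: N = 5,000 (section 5.2). The recruitment arithmetic agrees: 9 × 556 = 5,004.
- Retention: r = 85% (target, section 5.5.2) or 70% (assumed for power, section 10.6). Follow-up occasions are 5,000 × 0.85 = 4,250 or 5,000 × 0.70 = 3,500.
- STI sampling at baseline and at 6 months (section 5.4.3).
- HIV testing at both visits, at 6 months only if the baseline test was negative (section 5.1). The count below ignores the few not retested.
- The rapid HIV test is part of the randomized intervention, and the synopsis requires randomization just before that intervention. Baseline HIV sampling therefore falls inside the capture window, as does all 6-month sampling.

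**Share of sampling that precedes capture, if all baseline STI samples precede randomization**

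| Counting rule | Formula | r = 85% | r = 70% |
|---|---|---|---|
| STI sampling only | N / (N + rN) | 5,000 / 9,250 = 54.1% | 5,000 / 8,500 = 58.8% |
| HIV and STI counted separately at both visits | N / (2N + 2rN) | 5,000 / 18,500 = 27.0% | 5,000 / 17,000 = 29.4% |
| Baseline STI, baseline HIV, one joint follow-up occasion | N / (2N + rN) | 5,000 / 14,250 = 35.1% | 5,000 / 13,500 = 37.0% |

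**Sensitivity to the order.** Let s be the share of baseline STI sampling done before randomization. More than half of STI sampling precedes capture only if sN / (N + rN) > 0.5, that is, if s > (1 + r)/2. This requires s above 92.5% at 85% retention, or above 85% at 70% retention. The protocol does not allow s to be estimated, because the synopsis permits other orders and section 5.3.3 permits routine-care tests.

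**What the start rule covers.** Sections 5.4.7, 7.11 and Table 1 say when events are collected. None excludes an event because the sample that caused it was taken before randomization. None tells staff to look back either. Three cases follow:
- An event still present, or reported, after randomization can be recorded.
- An event that resolves before randomization and is not mentioned later has no stated capture. The two-visit option in section 5.4 makes this more likely.
- An event in a person sampled but never randomized has no stated capture. The number of such people is not given.

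**The case against.** The strongest reply is that little is lost. The samples are blood, urine and swabs from people already attending an STD clinic. Randomization will often be on the same day, so a reaction such as irritation may still be present or be mentioned afterwards. The synopsis collects AEs at each research visit. Section 7.11 defines an AE by the course of the trial and requires reporting of deaths during study participation, and section 5.1 enrolls people at consent. Events before randomization cannot bias the comparison of arms. Starting at randomization is also stated consistently in three places, so it could be a deliberate choice.

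Most of this stands, and it limits the point to a minor one. It does not remove it. The synopsis sentence conflicts with the three operative statements whenever the first visit ends before randomization. The flexible order permits STI sampling after randomization but does not require it, and section 10.2 states the reverse. Even with full flexibility, the synopsis keeps the baseline ACASI before randomization, and section 7.11 makes events from assessments reportable.

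A reader might infer that more than half of all sampling occasions fall outside safety capture. The documents do not support that. The figure holds for STI sampling alone under the section 10.2 order, while section 7.11 names HIV samples as well. Preceding the start of capture is also not the same as being excluded from it. A reader might further infer that the DSMB is given the wrong denominator, but the protocol states no AE denominator.

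**Conclusion.** The sections do not fit together. Events from STI sample collection are reportable, yet capture is stated to begin after randomization, and the described order takes the baseline STI samples before it. If that order is followed for everyone, about 5,000 baseline STI sampling occasions precede the start of capture: 54% to 59% of STI sampling, or roughly 27% to 37% of HIV and STI sampling together, depending on how occasions are counted. These shares assume 5,000 randomized, 70% to 85% retention and no use of the flexible order or of routine-care tests; either would lower them.

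The real gap is narrower than these shares. It consists of transient events that resolve before randomization and any events in people sampled but never randomized. Its size cannot be given, because the protocol states neither event rates nor the number sampled without being randomized. Severity is minor: the completeness of the safety record is affected, and the treatment comparison is not.

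**What to change.** Start AE and SAE capture at written informed consent, before the first study sample, in section 5.4.7, section 7.11 and the AE/SAE row of Table 1. Bring the synopsis statements on visit order and AE collection, the reportable-event list in 7.11 and the sequence in section 10.2 into line with that start. List events before randomization separately, not by arm, and include people who were sampled but not randomized.

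The cost is a few wording changes, one pre-/post-randomization flag on the AE form and a small extra reporting load at sites. The primary analysis is unchanged.

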5.4.8 Survey of Counselors and Intervention Recordings

As previously mentioned, we will conduct a brief survey of counselors (and back-up counselors) prior to randomizing study participants and after the intervention is completed to garner basic information about counselors' demographics, level of experience with HIV testing and prevention counseling, and attitudes and beliefs about HIV testing. Because it is the counselor's role in the study to provide the two study interventions, the study team wants to be able to describe counselor characteristics which will be reported in the primary outcome manuscript to give the context of study implementation. In addition, a planned secondary analysis will examine whether there is significant variability in treatment effects at different sites and whether counselor characteristics and attitudes may be related to these differences. While intervention sessions will be audio-recorded for the purpose of monitoring intervention fidelity, they may also be analyzed to describe how the sessions were conducted. In addition, we will examine whether participation in the trial has a significant effect on counselor attitudes.

